Comparison of Outcomes between the Use of Silverlon® Dressing and AQUACEL® AG dressing Post Cardiac Device Implant

Principal Investigator:

[name] FACC Director Center for Excellence in Atrial Fibrillation & Electrophysiology Research, Electrophysiologist, Professor, Department of Internal Medicine, University of Kansas Medical Center, Kansas City, KS 66160

Signature of PI:	Date:
------------------	-------

Co-investigators:

[name] MBBS [name] MD [name] MD [name] MD [name] MD [name] NP [name] MBBS [name] MD

Research and IRB site:

University of Kansas Medical Center Human Subjects Committee [name]

Study Sponsor: None.

Funded by: None.

Revised 22 January 2016

Protocol Summary

Silver impregnated dressings have been used widely since their introduction in the 1990s. A few studies have been done which showed that they may decrease the risk of post-operative infections of the wound sites. As a result of these studies there are several commercial available options, however we do not have any data on which ones are better. However, many aspects of the patient and the surgical wound may influence outcomes with respect to each dressing, one product may be more suitable for some patients. For example, given their lax skin texture, dressings with less adhesive may be better for elderly patients. This protocol describes our aim to prospectively study the two widely used dressings (namely Silverlon® and AQUACEL®AG) used at the University of Kansas Hospital for post-operative wound coverage and to assess which one has better patient outcomes.

Background

Implantation of cardiac implantable electronic devices has exploded in recent years. A nationwide analysis revealed that from 1997 through 2004, the number of pacemaker implants increased by 19% and that of automated implantable cardioverter defibrillators (AICDs) increased by 60% (1). Although cardiac implantable electronic devices (CIEDs) have made significant impacts in outcome of majority of implanted patients, these devices bought us a whole new set of problems due to both hardware issues and programing issues. Infections related to these devices have also increased from 5,308 in 2003 to 9,948 in 2011. The average mortality rate is 4.5% for patients with device infections which is high (2).

There are numerous ways of minimizing the rate and severity of post-operative infections. These include sterile technique including appropriate hand washing techniques, intra operative antibiotic administration, appropriate wound care and post-operative antibiotic coverage. Infections do happen and there is a continued need to improve all aspects of the surgery and post-operative care. Wound coverage with appropriate dressings is one aspect that has not been studied in the CIED implant patient population.

Silver is a well-known bacteriostatic agent. Silver impregnated dressings as opposed to standard dressings have been shown to reduce post-operative infections in patients post-CABG (3), post-laminectomy (4) and even post colo-rectal surgery (5). The above data was obtained from randomized studies using the Silverlon® dressings (short for Silver Nylon dressings). AQUACEL®AG, a product which touts a combination of patented Hydrofiber® Technology with ionic silver. The Hydrofiber® Technology has been shown to form a gel on contact with body fluids. This happens inside of the wound crevices and eliminating these crevices which could potentially be home for bacteria. AQUACEL® AG in in-vitro studies has been shown to be more effective than non-silver impregnated dressings (7, 8). It has been shown to be more effective post Incision and Drainage (I & D) of abscesses compared to iodoform (9).

Another aspect of wound care that is important is how easily dressings can be removed from of the wound at the time of dressing removal; 7 to 10 days post procedure. Some dressings are easier to remove than others. For example AQUACEL® AG has been shown to be less traumatic at removal than povidone iodine gauze, a dressing that was widely used in the past (10).

Rationale and Justification

Given our two options of the dressings, and lack of evidence on which of these is a better option for our post-operative Cardiac Implantable Electronic Device (CIED) implant patients, we sought to conduct a prospective study of outcomes with the Silverlon and Aquacel dressings.

Description of the Research Project

Objectives

- To assess the efficacy of each of the two dressings (Silverlon® and AQUACEL® AG) in preventing post-operative wound infections (primary outcome).
- 2. To assess the safety of each of the two dressings in terms of traumatic skin tears at the time of removal (secondary outcome).
- 3. To assess end points such as patient comfort at the time of removal (using a 1-10 pain scale), ease of removal (using a 1-5 scale completed by the operator), adherence of

the dressing at the post-op incision check 7 to 10 days post procedure (secondary outcome).

 To access skin breakdown and assigning a category/stage 1 – IV (using the National Pressure Ulcer Advisory Panel Pressure Ulcer States and Categories)

Design

This is a single-center, prospective, 2-arm randomized, non-blinded study involving about 200 patients total, 100 patient in the Silverlon arm and 100 patients in the AQUACEL® AG arm.

Location:

This study will be conducted at the University of Kansas Hospital, Kansas City, KS and Mid-America Cardiology locations.

Study inclusion and exclusion criteria

Inclusion:

- 1. All patients aged 18 or more who can give valid informed consent.
- 2. All patients who are scheduled for a CIED implant, generator change, upgrade at the University of Kansas Hospital.

Exclusion:

- 1. Patients who are already on antibiotics for another reasons.
- 2. Immunocompromised patients such as those on immunosuppressant's and HIV positive patients.
- 3. Patients who are post device explant for lead infection.
- Patients with an allergy to adhesive, silver or an allergy to the dressing(s) or their components.

Subject Enrollment

Potential subjects at the University of Kansas Hospital will be identified from daily EP procedure list. Subjects will be before their procedure or while in clinic for pre-op visit. All eligible patients will be offered to participate irrespective of sex, age, race, ethnicity or disability.

Subject Consent

Informed consent will be obtained from each patient. Participation in this study is voluntary and subject can decline at any stage. Participation in this study will have no impact on the patient's relationship with Mid America Cardiology or University of Kansas Hospitals or their associated facilities. After explaining the risks and benefits, informed consent will be obtained to participate in the study. They will be randomized into either Silverlon or AQUACEL® AG arm.

Randomization:

Block randomization will be used to permit uniform sample sizes at the end of our study. Randomization will be done with the aid of a computer based algorithm.

Intervention:

Arm 1:Subjects randomized to this arm will receive Silverlon® dressing post operatively. Arm 2: Subjects randomized to this arm will receive AQUACEL® AG dressing post operatively.

Follow-Up:

No modifications are required for follow-up visits. All subjects will have their dressing evaluated in the cardiology office for an incision check at 7-10 days post procedure.

Photographs:

Photographs of the incision site will be taken immediately post-procedure and during the 7-10 days post procedure visit. Images of the incision site and the area immediately surrounding it will be visible. No identifying features of the patient will be visible in the photographs. The purpose of the photographs is to document the appearance of the skin surrounding the wound. Photographs will taken by the separate performing the incision check on a digital camera that is kept in a secure, locked cabinet when the camera is not in use. Images will be labeled with the subject number, stored electronically (.jpg, .png or other relevant format) and uploaded to the secure KUMC server. Photographs may be used for finitely.

Data Collection

The following variables will be collected by electronic medical record query or during the interview with the subject. Patient information will be coded with the following system: 001,002,003 etc.

Variables:

- 1. Demographics: Age, Sex, Race, Height, Weight, BMI.
- 2. Past Medical History: HTN, CAD, Thyroid status, OSA, DM, HLD, CVA, CKD, Valvular Diseases, Smoking History, COPD, CHF, peripheral vascular disease
- 3. Medication History: Antiplatelet agents, anticoagulants, steroids, hypoglycemic,
- 4. Indication for procedure.
- 5. Procedure notes.
- 6. Complications including post op hematoma
- 7. Discharge medications including antibiotics used for generator exchanges
- 8. Follow up post op Day 7 -10: Appearance of skin surrounding wound including grading of swelling (mild swelling compared to the contralateral side vs significant swelling), presence of any erythema (compared to skin on the contralateral side), patient comfort level (from 1-5). Incidence of frank infection and ease of dressing removal (from 1-5) by nurse practitioner, Skin laxity (firm skin vs lax skin which is prone to tearing), presence

or absence of leg edema (a surrogate indicator of subcutaneous edema at the wound site which would predispose to evisceration of skin at the time of dressing removal)

Statistical Considerations

The primary efficacy outcome of the study is the prevention of infection. Secondary outcomes include the side-effects such as trauma at the time of removal, ease of removal and patient discomfort at the time of removal.

Standard statistical tools will be utilized. SPSS and STATA® version 9.0 will be used to analyze the data. Continuous data will be described as the mean value \pm SD, and categorical data will be described as frequencies. The association between a clinical event/ endpoint and specific clinical and laboratory variables will be evaluated using the t test for continuous variables or the Fischer exact test for categorical variables. A p value <0.05 will be considered statistically significant.

Confidentiality

The data will be collected on data sheets and will be stored in a locked cabinet. This data will be transferred to an access database within the KUMC Cardiovascular Research Institute, which has a secure password protected main frame. Once all the data is analyzed, the data will be deleted and the paper records will be shredded.

Study Records

All records relative to the research will be treated in confidence and stored in the CVRI Department. The records will be available only to the investigators and any agents of the University or federal government who oversee research involving human subjects.

Safety Monitoring

All incidences of serious adverse events observed will be reported to the principal investigator. These events will be reviewed against the HSC reporting criteria; all events meeting the reporting criteria will be forwarded to the HSC.

Risks, Benefits and Justification of the Research Study

Risks:

There are no additional risks for patients that participate in this study. Each of the patients would have received one of the two dressings even if they were not part of this study.

Benefits:

This study will help in identifying new methods of improving the efficacy and outcomes of the dressings used for CIED patients at the University of Kansas Hospital.

References

2. HCUPnet. Healthcare Cost and Utilization Project (HCUP). 2006-2009. Agency for Healthcare Research and Quality, Rockville, MD. http://hcupnet.ahrq.gov/ Accessed 2014.

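### The protocol does not say when the allocation is opened or how it is concealed, so the arm may be known before and during the procedure; it could be opened at skin closure at little cost

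*Combined protocol and SAP*

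**What the plan says.** The Design section describes the trial: "This is a single-center, prospective, 2-arm randomized, non-blinded study involving about 200 patients total". On the approach to patients, the Subject Enrollment section says "Subjects will be before their procedure or while in clinic for pre-op visit" (a verb is missing, but the two settings are clear). The Subject Consent section says "After explaining the risks and benefits, informed consent will be obtained to participate in the study", and its next sentence is "They will be randomized into either Silverlon or AQUACEL® AG arm".

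The Randomization section has two sentences: "Block randomization will be used to permit uniform sample sizes at the end of our study" and "Randomization will be done with the aid of a computer based algorithm". It gives no block size, no time at which the allocation is generated or released, no list-holder and no concealment rule. Under Intervention, the first arm is described as "Subjects randomized to this arm will receive Silverlon® dressing post operatively", and the second arm has the same timing.

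The Subject Consent section lets patients decline at any stage. The Statistical Considerations section defines no analysis population.

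**The concern.** The allocated treatment is not needed until the wound is closed. Any earlier release of the allocation creates an interval in which the arm is known but has no use.

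Two things can go wrong in that interval. First, staff who know the arm may treat patients differently during the procedure. The primary outcome is infection, and the Background section lists intra-operative antibiotics, sterile technique and wound care among its determinants. Second, a patient may withdraw, be cancelled, or start antibiotics for another reason (an entry exclusion) after the arm is known. With no analysis population defined, nothing settles whether such a patient is still counted. If losses of this kind depend on the arm, the randomised comparison is no longer protected. A larger sample would cure neither problem.

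**Working it through.** **1. Order of events.** No stated figure can be reproduced here, so the sections are set side by side.

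| Step | Section | Timing given |
|---|---|---|
| Approach | Subject Enrollment | Before the procedure or at the pre-operative visit |
| Consent | Subject Consent | Before randomisation |
| Randomisation | Subject Consent; Randomization | Mentioned after consent; no time stated |
| Release of the allocation | None | Not stated |
| Dressing applied | Intervention | After the operation |
| Outcome check | Follow-Up | 7-10 days after the procedure |

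The text permits release at any point from consent to dressing. Nothing rules out the early end of that range.

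**2. Sensitivity of the primary outcome.** With 100 patients per arm, one infection moves an arm's rate by 1/100, or one percentage point. With no infections in one arm, a two-sided Fisher exact test first reaches p < 0.05 at 6 infections in the other. A few patients treated differently, or lost selectively, could therefore matter.

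**3. Predictability of blocks.** In an open trial with one fixed 1:1 block size of 2m, the share of allocations known with certainty from those before is 1/(m + 1):

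- size 2: 1/2 = 50%
- size 4: 1/3 = 33%
- size 6: 1/4 = 25%

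The block size is not stated, so these figures are conditional. They show why late opening needs varying block sizes as well. They do not measure the timing problem itself.

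**4. Precision lost before closure.** The documents give no loss rate. Assume a fraction d of 200 allocated patients is lost before closure and not replaced. The standard error is multiplied by 1/√(1 − d), and keeping 100 per arm would need 100/(1 − d), rounded up.

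| Assumed d | Lost of 200 | SE factor | Needed per arm |
|---|---|---|---|
| 5% | 10 | 1/√0.95 = 1.026 | 100/0.95 = 105.3, so 106 |
| 10% | 20 | 1/√0.90 = 1.054 | 100/0.90 = 111.1, so 112 |

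Exact two-sided Fisher power at α = 0.05, under assumed infection rates:

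| Assumed rates | 100 per arm | 95 per arm | 90 per arm |
|---|---|---|---|
| 5% vs 2% | 9.6% | 8.6% | 7.7% |
| 10% vs 2% | 58.7% | 55.3% | 51.9% |

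The largest fall is 58.7 − 51.9 = 6.8 percentage points.

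**5. Arm balance.** If 20 of 200 are lost at random, the number lost from one arm has SD √(20 × 0.5 × 0.5 × 180/199) = 2.1. A split of 88 and 92 has efficiency 4 × 88 × 92/180² = 0.9995 relative to 90 and 90. Chance losses therefore do not seriously upset the aim of equal arms.

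**6. What opening at closure covers.**

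| Source of bias or loss | Covered? |
|---|---|
| Care during the procedure, up to closure | Yes, if the list is concealed and not predictable |
| Cancellation, withdrawal or ineligibility before closure | Yes; the patient is never randomised |
| Post-operative and discharge antibiotics | No |
| Loss between closure and the 7-10 day visit | No |
| Unmasked recording of infection and removal | No |

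**The case against.** The strongest objection is that sentence order in a consent paragraph is not a schedule. A reader might infer that patients are randomised straight after consent. The documents do not establish this, since the text is equally compatible with opening the allocation when the dressing is applied. That stands. The supportable finding is that timing and concealment are unspecified, so early knowledge of the arm is permitted.

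A reader might also infer that late opening removes both differential care and loss after allocation. It does not. The antibiotic item in Data Collection, "Discharge medications including antibiotics used for generator exchanges", concerns discharge, which comes after closure. Patients may still decline before the outcome visit, and the nurse practitioner's assessment there has no masking described.

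Nor does the plan say that a randomised patient who later starts antibiotics is excluded; antibiotic use is an entry criterion only. The gap is the missing analysis population, which needs its own sentence whatever the timing.

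Finally, performance bias is possible but not shown. Both dressings contain silver and are already in use at the hospital, and no operator preference between them is documented. For patients identified from the daily procedure list, the interval may be short. These points limit the likely size of the bias. They give no reason to leave the allocation open during the procedure.

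**Conclusion.** The point holds in limited form. The protocol neither times nor conceals the allocation, so in this non-blinded trial the arm may be known before and during the procedure, although it is needed only afterwards. Opening a concealed allocation at closure is more resistant to bias and should be adopted.

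The size of any bias cannot be calculated from the documents. The measurable cost of losses before closure is small: a 2.6% to 5.4% rise in standard error if 5% to 10% are lost without replacement, and under 7 points of power in the scenarios tried. Both the loss rates and the infection rates are assumptions. The case rests on avoiding bias, with little to gain in precision or arm balance.

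**What to change.** In the Subject Consent section, replace the randomisation sentence with: *Consented patients will be randomised after skin closure, immediately before the dressing is applied; the allocation stays concealed until then.*

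In the Randomization section, state that the computer list uses randomly varying block sizes and is held by someone who neither enrols nor operates. In Statistical Considerations, state that all randomised patients are analysed in their assigned arm.

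Post-operative antibiotic decisions, losses after closure and unmasked assessment remain and need to be handled separately.

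The cost is a few sentences and a later run of the planned algorithm. Both dressings must be in the procedure room, and someone must open the allocation at closure. Reaching 200 randomised patients would also require consenting somewhat more: under the assumed 5% to 10% loss, 200/0.95 = 210.5 to 200/0.90 = 222.2, or about 211 to 223.

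### Does the primary outcome, infection called without written criteria at an open-label Day 7-10 visit, require a change to the plan?

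*Combined protocol and SAP*

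**What the plan says.** The Objectives make the efficacy of each dressing "in preventing post-operative wound infections (primary outcome" the first aim, and Statistical Considerations repeats it: "The primary efficacy outcome of the study is the prevention of infection". Neither section defines a case.

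The explicit variable is in Data Collection, Variables item 8, at post-operative Day 7-10: "Incidence of frank infection and ease of dressing removal (from 1-5) by nurse practitioner". The same item separately records swelling at two levels ("mild swelling compared to the contralateral side vs significant swelling") and redness ("presence of any erythema (compared to skin on the contralateral side"). Item 6, "Complications including post op hematoma", is open-ended and could also capture an infection.

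On masking, Design states: "This is a single-center, prospective, 2-arm randomized, non-blinded study". On timing, Follow-Up states: "All subjects will have their dressing evaluated in the cardiology office for an incision check at 7-10 days post procedure". Photographs plans images of the incision site right after the procedure and at the Day 7-10 visit, labelled by subject number, to document the surrounding skin. No masked read is planned.

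Statistical Considerations names Fisher's exact test for categorical variables at the 0.05 level. Design gives 100 patients per arm.

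**The concern.** A primary outcome normally has a stated case definition. Here one undefined term carries it, and nothing says which sign or combination of signs makes a case. The trial is open-label, and the dressing is evaluated and its removal scored at the same visit, so the assessor very probably knows the arm (an inference; the text does not say so).

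The recorder is also not fully settled. The nurse practitioner in item 8 may make the infection call or only score ease of removal, which the Objectives assign to the operator. Data Collection allows variables to come from a record query or an interview without saying which applies to infection.

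If calls differed by arm, the primary comparison would be distorted. With probably few events, a handful of judgements could matter. The remedy considered was a tick-box rule with a fixed recorder, plus a masked read of the Day 7-10 photographs as supportive evidence.

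**Working it through.** **Inputs.** From the documents: 100 per arm (Design), Fisher's exact test and the 0.05 level (Statistical Considerations). Assumed: a two-sided test, and every infection and false-call rate below. The plan states no rate, effect size or power, so there is no figure of its own to reproduce.

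**1. Weight of one call.** Each call moves an arm's risk by 1/100, or 1 percentage point. With assumed counts of 3 vs 3, one extra call gives 4 vs 3 and a risk ratio of 4/3 = 1.33 instead of 1.00. The Fisher boundary lies between these neighbours:

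| Counts | p | One more call | p |
|---|---|---|---|
| 5 vs 0 | 0.059 | 6 vs 0 | 0.029 |
| 7 vs 1 | 0.065 | 8 vs 1 | 0.035 |
| 10 vs 3 | 0.082 | 11 vs 3 | 0.049 |

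**2. How often the table lies within one call of the boundary.** Sum the product of two binomial probabilities (n = 100 each) over all tables where adding or removing one case in either arm changes significance.

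| Assumed true rates | Probability |
|---|---|
| 1% vs 1% | 0.3% |
| 2% vs 2% | 2.2% |
| 3% vs 3% | 4.5% |
| 5% vs 5% | 5.8% |
| 10% vs 10% | 4.6% |
| 5% vs 1% | 31% |
| 8% vs 2% | 35% |
| 10% vs 3% | 31% |

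Closeness to the boundary is therefore uncommon only if the arms have equal rates. These figures also do not measure the defect: they describe Fisher's test at this sample size and would be the same with perfect criteria and masked assessors.

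**3. Arm-dependent calling.** This is the relevant mechanism. Let both arms have true rate p, with all true cases found and false calls made at rate f in one arm only. The observed rates are p and p + (1 − p)f. For p = 2% and f = 5%, the second is 0.02 + 0.98 × 0.05 = 0.069. The probability of p < 0.05 is:

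| True rate | f = 0 | f = 2% | f = 5% |
|---|---|---|---|
| 1% | 0.0004 | 0.033 | 0.31 |
| 2% | 0.005 | 0.042 | 0.26 |
| 3% | 0.011 | 0.045 | 0.22 |

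At p = 2%, f = 5% means 98 × 0.05 = 4.9 expected false calls in one arm and none in the other, against 2 expected true cases. At f = 2% it means 98 × 0.02 = 1.96, and the rejection probability stays below 0.05. A material effect thus needs false calls that outnumber the true infections and fall in one arm only. Nothing in the documents shows that this would happen.

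**4. What each part of the remedy would alter.**
- *Written rule.* Its content would be left to the investigators. Item 8 already lists redness and swelling apart from frank infection. The natural reading is that the infection call means overt infection, judged clinically at the incision check, and not redness or swelling alone. A written rule may narrow discretion, but the call remains unmasked and no different result can be derived from a rule with no stated content.
- *Masked photograph read.* It would cover about 200 images as support only. Redness is defined against the opposite side, and the swelling grade also refers to that side; the planned images show only the incision area, so both would have to be left out. Warmth, tenderness and deep infection are not visible. The primary analysis would be unchanged.

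**The case for a change.** The strongest case for a change is that a primary result without a case definition is hard to reproduce or interpret, whatever its p-value. The Objectives give skin breakdown, which is not the primary outcome, a named published staging system but give infection none. Expectations could also be unequal: the Background credits Silverlon with fewer infections in randomized studies, while for AQUACEL AG it cites in-vitro work, an abscess comparison and easier removal. Later repair is limited, since Confidentiality says the data will be deleted and the paper records shredded after analysis. The written rule is cheap: a few form fields and no new visit.

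Much of this stands. The definition is missing from the protocol, the recorder and data source are ambiguous, and a rule on paper would be good practice. Other parts are weaker. A nurse practitioner is already named, so the recorder is unclear rather than absent. Redness, swelling and photographs are kept until analysis, so partial reclassification is possible. The data sheets mentioned under Confidentiality are not in the documents and may carry more detail. Excluding culture results from the rule while keeping bedside judgement would be a preference. A reader with no access to allocation is also not assured, because Study Records opens the records to the investigators.

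**Conclusion.** The observation is correct, but no change to the plan follows. The missing definition is a gap that the investigators can fill sensibly at the incision check, using the signs item 8 already collects; the unclear recorder and data source are drafting ambiguities of the same kind. The masked photograph read offers too little for about 200 gradings, since it omits redness and swelling as now photographed and leaves the unmasked bedside call primary.

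The possible effect is not negligible. False calls in 5% of uninfected wounds in one arm only would give a significant result with probability 0.22 to 0.31, and in 2% with probability 0.03 to 0.05. Both ranges rest on assumed equal true rates of 1% to 3%, complete detection of true cases and a two-sided Fisher test at 100 per arm. The documents supply no infection rate, no error rate and no evidence of arm-dependent calling, so the size and direction of any actual bias remain unknown. The result should be read as an open-label clinical judgement of infection at Day 7-10.

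### Skin laxity is graded only at the dressing-removal visit and described by its liability to tear, so a tear can influence the grade

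*Combined protocol and SAP*

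**What the plan says.** - **Variable and timing.** Skin laxity appears in the Variables list of Data Collection only in item 8, the day 7-10 follow-up: "ease of dressing removal (from 1-5) by nurse practitioner, Skin laxity (firm skin vs lax skin which is prone to tearing"). It is not among the demographic, history, medication or procedure items. Being liable to tear is the only description given of lax skin.
- **Removal.** Background places removal in the same window: "at the time of dressing removal; 7 to 10 days post procedure".
- **Outcome.** The second objective assesses safety "in terms of traumatic skin tears at the time of removal (secondary outcome").
- **Analysis.** Statistical Considerations says: "The association between a clinical event/ endpoint and specific clinical and laboratory variables will be evaluated using the t test" for continuous variables, or Fisher's exact test for categorical ones, with significance at p<0.05. The variables are not listed and laxity is not named.
- **Why laxity is of interest.** The Protocol Summary says that "many aspects of the patient and the surgical wound may influence outcomes with respect to each dressing, one product may be more suitable" in certain groups, and gives as its example that "given their lax skin texture, dressings with less adhesive may be better for elderly patients".
- **Earlier contact.** Subject Enrollment already provides for meeting patients "before their procedure or while in clinic for pre-op visit".

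**The concern.** A patient characteristic used to explain an outcome should be fixed before the outcome is seen. Here both are recorded at one visit in a non-blinded study, and the lax category is described by the very event that may just have occurred. A grader who has seen the skin tear has direct evidence for that label. No section says that laxity is graded first, on other skin, or by someone unaware of the tear. Swelling and erythema are compared with the contralateral side; laxity has no such reference.

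At stake is any laxity-tear association tested under the general analysis sentence, and any later laxity subgroup result. Such a result bears on the Summary's question of which patients suit which dressing. Age, the marker of the Summary's example group, is collected under Demographics and is not affected.

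**Working it through.** The plan gives no figure for laxity, tears or their association, so there is nothing to reproduce. The timing was checked by reading; only the size needs arithmetic.

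**Inputs from the documents.** 100 patients per arm (Design); Fisher's exact test, p<0.05 (Statistical Considerations). Sidedness is not stated; two-sided is assumed.

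**Assumed inputs.** Tear risk 10% in one arm and 5% in the other; true lax share L = 40%; grading after removal; a share q of torn firm-skin patients graded lax because of the tear. Untorn patients are graded correctly.

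**Patients misgraded, no true laxity effect.** Expected tears: 100 × 0.10 + 100 × 0.05 = 15. In firm skin: 15 × 0.60 = 9. At q = 0.1, 0.2 and 0.3 the number regraded is 0.9, 1.8 and 2.7, or about 1, 2 and 3 of 200.

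**Recorded odds ratio.** With s the truly lax share of torn patients,

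recorded OR = true OR × [1 + q(1 − s)/s] / (1 − q).

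With no true effect, s = 0.40 and (1 − s)/s = 1.5:

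- q = 0.1: 1.15/0.9 = 1.28
- q = 0.2: 1.30/0.8 = 1.63
- q = 0.3: 1.45/0.7 = 2.07

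Direct check at q = 0.2: torn patients are 6 + 1.8 = 7.8 lax and 7.2 firm; the 185 untorn are 74 lax and 111 firm. (7.8/7.2)/(74/111) = 1.63.

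**Chance of p<0.05 with no true effect.** Arms pooled, recorded laxity against tear, 100,000 simulated trials per cell:

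| Tear risks; lax share | q=0 | q=0.1 | q=0.2 | q=0.3 |
|---|---|---|---|---|
| 10% v 5%; 40% (base) | 3.7% | 5.8% | 12.4% | 23.5% |
| 5% v 2.5%; 40% | 2.7% | 4.4% | 7.4% | 12.7% |
| 10% v 5%; 60% | 3.5% | 4.1% | 6.1% | 10.2% |
| 5% v 2.5%; 60% | 2.8% | 2.9% | 3.5% | 4.8% |
| 20% v 10%; 40% | 4.0% | 8.0% | 20.5% | 41.2% |
| 10% v 5%; 20% | 3.4% | 10.8% | 27.4% | 50.1% |

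If tears are rarer still (2% v 1%), the chances at q = 0.1/0.2/0.3 are 1.8/2.6/4.6% with 40% lax and about 0.9/0.7/0.6% with 60% lax. Exact enumeration of the possible tables, in place of simulation, agrees with all these figures to within 0.4 of a percentage point.

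**True laxity odds ratio of 2** (closer to the protocol's premise), other base inputs and each arm's overall tear risk held. Now s = 0.557, (1 − s)/s = 0.795, and the pooled true OR is 1.99:

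- q = 0.1: 1.99 × 1.080/0.9 = 2.4
- q = 0.2: 1.99 × 1.159/0.8 = 2.9
- q = 0.3: 1.99 × 1.239/0.7 = 3.5

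The chance of p<0.05 (50,000 trials per cell) is 32%, 44% and 58%, against 21% at q = 0. With tear risks halved it is 17%, 24% and 31%, against 12%.

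**Subgroups.** A grade that responds to tears is also a post-randomisation variable. If tear risks were 5% and 15%, 30% were truly lax and q were 0.25, the shares graded lax would be 0.30 + 0.70 × 0.25 × 0.05 = 30.9% and 0.30 + 0.70 × 0.25 × 0.15 = 32.6%: a small imbalance caused by the outcome.

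**After the change.** Grading before removal sets q = 0, so the q = 0 figures apply.

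**The case against.** The strongest objection is that no planned analysis is shown to be harmed. The plan names no laxity test, subgroup or adjustment; that laxity is one of the unlisted variables is an inference from its being collected. This stands, and it is a main reason for the low weight.

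Second, "Skin laxity (firm skin vs lax skin which is prone to tearing") may only say why a risk marker is recorded. The next item, leg edema, is explained in a similar way, and firm against lax is a judgement of texture. The list order is not a rule, so the nurse may well grade first. This weakens the point but does not remove it: no other criterion is given, and nothing secures a grade before removal. The post-procedure photograph precedes removal, but its stated purpose is the appearance of the skin around the wound, not a laxity grade.

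Third, the size rests wholly on assumptions. It needs grading after removal and regrading because of the tear. The largest error rates need doubled tear risks or only 20% lax, with q = 0.3. With rare tears the error rate stays below 5%, although the odds ratio is still biased. All of this stands.

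Fourth, item 8 does not list skin tear as a variable of its own, and settling how that outcome is recorded comes first. That is fair, but it does not answer this point.

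**Conclusion.** The concern holds as a minor design point. The documents put the laxity grade and the tear outcome in the same visit window, describe lax skin by its liability to tear, and do not secure a grade before removal. They show that a tear can influence the grade, not that it will.

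Because tears are likely to be few, a handful of misgraded patients matters. In the assumed base case, 1 to 3 of 200 move the expected odds ratio from 1.0 to between 1.28 and 2.07, and the chance of a spurious significant result from about 3.7% to between 5.8% and 23.5%. Across the other assumed inputs that chance runs from under 1% to 50%. A real association would be overstated: a true odds ratio of 2 would be recorded as 2.4 to 3.5. The primary infection outcome and the randomised comparison of tears do not use laxity and are unaffected.

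**What to change.** Grade skin laxity at consent or the pre-op visit, before the allocation is known, using a description of the skin that does not refer to tearing. At the least, grade it before the dressing is removed; that alone prevents the tear from influencing the grade. Add one sentence to Statistical Considerations saying that any association or subgroup analysis of removal outcomes uses this grade.

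The cost is one item moved to the baseline form, a change of its wording, and a short examination (about a minute, assumed) at an existing contact. A pre-op grade will not reflect swelling at the wound by day 7-10, but item 8 already records swelling separately. The change should be made before patients are graded, because a pre-tear grade cannot be recovered once a tear has been seen.
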